## 12.0 SAFETY OVERSIGHT

### 12.1 Study monitoring

The study team will perform internal quality management of study conduct, data and biological specimen collection, documentation and completion according to institutional policies.

Any study under the purview of the University of Virginia IRB-HSR is subject to review of files at the University of Virginia. Studies are chosen for Post-approval Monitoring either a) at random or b) requested by a study team member or any member of the IRB-HSR.

The purpose of Post-approval Monitoring audits is to ensure that documentation of clinical research studies is of the highest quality, verify protocol adherence, and ensure that all Federal and local rules concerning clinical research are being fulfilled. Post-approval monitoring is done by staff within the office of the Vice President for Research (VPR) in accordance with their Standard Operating Procedures. The conduct of an on-site review may include but is not limited to:

- requests for progress reports from investigators,
- examinations of research records, including signed informed consent documents, protocol modifications, and unexpected, serious, and/or related adverse experience reports,
- contacts with research subjects, or
- observation of the consent process and/or research procedures. Examples of when observation of the consent process could occur are:
  - Full board IRB determines during review of a project that a conflict of interest exists such that the informed consent process should be observed by a neutral party;
  - IRB is made aware of a complaint or concern with regard to the informed consent process; or
  - IRB determines as a result of the monitoring process that the consent process is insufficient and education/training is required for conduct of consent.

## 13.0 STOPPING DECISION RULES

The study enrollment will be stopped and reviewed by the PI if any of the following specific events occur or, if in the judgement of the study physician, subject safety is at risk of being compromised during the visit:

- Death due to study procedure
- Occurrence of a life threatening allergic/hypersensitivity reaction (anaphylaxis), manifested by bronchospasm with or without urticaria or angioedema requiring hemodynamic support with pressor medications or mechanical ventilation due to any of the study procedures performed (pulmonary function testing, blood collection)
- One subject with a grade 4 or persistent grade 3 ( $\geq 72$  hours) associated with study procedures

- Two subjects with persistent Grade 3 ( $\geq$  72 hours) or higher lab toxicity for the same parameter associated with study procedures
- An overall pattern of symptomatic, clinical, or laboratory events that the study investigators consider associated with study product and that may appear minor in terms of individual events but that collectively may represent a serious potential concern for safety.
- Any other event(s) which is considered to be a serious adverse event in the good clinical judgment of the attending physician team. This will be appropriately documented.

## **14.0 STUDY MANAGEMENT**

### **14.1 Institutional Review Board (IRB) Approval**

It is expected that the IRB will have the proper representation and function in accordance with federally mandated regulations. The IRB should approve the consent form and protocol.

### **14.2 Informed Consent**

Informed consent is a process that is initiated prior to the individual's agreeing to participate in the study and continues throughout the individual's study participation. Consent forms will be Institutional Review Board (IRB)-approved and the participant will be asked to read and review the document. A member of the study team will explain the research study to the participant and answer any questions that may arise. A verbal explanation will be provided in terms suited to the participant's comprehension of the purposes, procedures, and potential risks of the study and of their rights as research participants. Participants will have the opportunity to carefully review the written consent form and ask questions prior to signing. The participants should have the opportunity to discuss the study with their family or surrogates or think about it prior to agreeing to participate. If the participant is deemed incapable of making their own medical decisions, a surrogate decision maker or legally authorized representative will be provided with the study information as detailed above and may consent to enrollment on behalf of the participant. The participant (or surrogate decision maker) will sign the informed consent document prior to any procedures being done specifically for the study. Both paper-based and electronic/e-consent approaches will be utilized as appropriate.

Results from procedures completed prior to consent for standard of care purposes may be used for research purposes.

Participants must be informed that participation is voluntary and that they may withdraw from the study at any time, without prejudice. A copy of the informed consent document will be given to the participants for their records.

The informed consent process will be conducted and documented in the source document (including the date), and the form signed, before the participant undergoes any study-specific procedures. The rights and welfare of the participants will be protected by emphasizing to them that the quality of their medical care will not be adversely affected if they decline to participate in this study.

### **14.3 Adherence to the Protocol**

Except for an emergency situation in which proper care for the protection, safety, and well-being of the study subject requires alternative treatment, the study shall be conducted exactly as described in the approved protocol.

#### **14.3.1 Emergency Modifications**

Investigators may implement a deviation from, or a change of, the protocol to eliminate an immediate hazard(s) to trial subjects without prior IRB-HSR approval/favorable opinion.

For any such emergency modification implemented, a UVA IRB modification form must be completed by study personnel within five (5) business days of making the change.

### **14.3.2 Other Protocol Deviations/Violations**

**Protocol Deviations:** A protocol deviation is any unplanned variance from an IRB approved protocol that:

- Is generally noted or recognized after it occurs
- Has no substantive effect on the risks to research participants
- Has no substantive effect on the scientific integrity of the research plan or the value of the data collected
- Did not result from willful or knowing misconduct on the part of the investigator(s).

Study personnel will record the deviation, and report to any sponsor or data and safety monitoring committee in accordance with their policies. Deviations should be summarized and reported to the IRB at the time of continuing review.

**Protocol Violations:** An unplanned protocol variance is considered a violation if the variance:

- Has harmed or increased the risk of harm to one or more research participants.
- Has damaged the scientific integrity of the data collected for the study.
- Results from willful or knowing misconduct on the part of the investigator(s).
- Demonstrates serious or continuing noncompliance with federal regulations, State laws, or University policies.

Violations should be reported by study personnel to the IRB within one (1) week of the investigator becoming aware of the event (refer to Table 2 in section 13 – Reporting Adverse Events and Protocol Deviations).

## **14.4 Obligations of Investigators**

The Principal Investigator is responsible for the conduct of the clinical trial at the site in accordance with Title 21 of the Code of Federal Regulations, all applicable local regulatory laws and regulations and/or the Declaration of Helsinki. The Principal Investigator is responsible for personally overseeing the treatment of all study subjects. The Principal Investigator must assure that all study site personnel, including sub-investigators and other study staff members, adhere to the study protocol and all FDA/GCP/NCI regulations and guidelines regarding clinical trials both during and after study completion. It is the responsibility of the Principal Investigator to ensure that all study site personnel are aware that the study protocol and all data generated is confidential and should not be disclosed to third parties (with the exception of local and national regulatory bodies which require access for oversight purposes). The Principal Investigator will be responsible for assuring that all the required data will be collected and entered onto the Case Report Forms. Periodically, monitoring visits will be conducted and the Principal Investigator will provide access to his/her original records to permit verification of proper entry of data. At the completion of the study, all case report forms will be reviewed by the Principal Investigator and will require his/her final signature to verify the accuracy of the data.

## **15.0 DATA HANDLING AND RECORDKEEPING**

### **15.1 Data Collection and Management Responsibilities**

Data collection is the responsibility of the clinical trial staff under the supervision of the Principal Investigator. The investigator is responsible for ensuring the accuracy, completeness, legibility, and timeliness of the data reported.

Clinical data (including adverse events (AEs), concomitant medications, and expected adverse reactions data) and clinical laboratory data will be entered into RedCap electronic database. Clinical data will be entered directly from the source documents.

All source documents should be completed in a neat, legible manner to ensure accurate interpretation of data.

## **15.2 Study Records Retention**

Study documents should be retained for a minimum of 2 years after the last approval of a marketing application in an International Conference on Harmonisation (ICH) region and until there are no pending or contemplated marketing applications in an ICH region or until at least 2 years have elapsed since the formal discontinuation of clinical development of the study intervention. These documents should be retained for a longer period, however, if required by local regulations. No records will be destroyed without the written consent of the IND sponsor, if applicable. It is the responsibility of the IND sponsor to inform the study team when these documents no longer need to be retained. Record retention will be in accord with 21 CFR 312.62 and HIPAA regulations.

## **15.3 Publication and Data Sharing Policy**

National Institutes of Health (NIH) Public Access Policy, which ensures that the public has access to the published results of NIH funded research. It requires scientists to submit final peer-reviewed journal manuscripts that arise from NIH funds to the digital archive [PubMed Central](#) upon acceptance for publication.

This study will comply with the NIH Data Sharing Policy and Policy on the Dissemination of NIH-Funded Clinical Trial Information and the Clinical Trials Registration and Results Information Submission rule. As such, this trial will be registered at ClinicalTrials.gov, and results information from this trial will be submitted to ClinicalTrials.gov. In addition, every attempt will be made to publish results in peer-reviewed journals.

## **15.4 Conflict of Interest Policy**

The independence of this study from any actual or perceived influence, such as by industry, is critical. Therefore, any actual conflict of interest of persons who have a role in the design, conduct, analysis, publication, or any aspect of this trial will be disclosed and managed. Furthermore, persons who have a perceived conflict of interest will be required to have such conflicts managed in a way that is appropriate to their participation in the design and conduct of this trial. The study leadership in conjunction with the institution has established policies and procedures for all study group members to disclose all conflicts of interest and will establish a mechanism for the management of all reported dualities of interest.

## APPENDIX:

### NIAID 8-POINT ORDINAL SCALE FOR CLINICAL IMPROVEMENT

- The ordinal scale is an assessment of the clinical status at the first assessment of a given study day. The scale is as follows: 8) Death; 7) Hospitalized, on invasive mechanical ventilation or extracorporeal membrane oxygenation (ECMO); 6) Hospitalized, on non-invasive ventilation or high flow oxygen devices; 5) Hospitalized, requiring supplemental oxygen; 4) Hospitalized, not requiring supplemental oxygen - requiring ongoing medical care (COVID-19 related or otherwise); 3) Hospitalized, not requiring supplemental oxygen - no longer requires ongoing medical care; 2) Not hospitalized, limitation on activities and/or requiring home oxygen; 1) Not hospitalized, no limitations on activities.

### NIH SEVERITY CATEGORIZATION

- *Asymptomatic or Presymptomatic Infection:* Individuals who test positive for SARS-CoV-2 using a virologic test (i.e., a nucleic acid amplification test or an antigen test) but who have no symptoms that are consistent with COVID-19.
- *Mild Illness:* Individuals who have any of the various signs and symptoms of COVID-19 (e.g., fever, cough, sore throat, malaise, headache, muscle pain, nausea, vomiting, diarrhea, loss of taste and smell) but who do not have shortness of breath, dyspnea, or abnormal chest imaging.
- *Moderate Illness:* Individuals who show evidence of lower respiratory disease during clinical assessment or imaging and who have saturation of oxygen ( $\text{SpO}_2$ )  $\geq 94\%$  on room air at sea level.
- *Severe Illness:* Individuals who have  $\text{SpO}_2 < 94\%$  on room air at sea level, a ratio of arterial partial pressure of oxygen to fraction of inspired oxygen ( $\text{PaO}_2/\text{FiO}_2$ )  $< 300$  mm Hg, respiratory frequency  $> 30$  breaths/min, or lung infiltrates  $> 50\%$ .
- *Critical Illness:* Individuals who have respiratory failure, septic shock, and/or multiple organ dysfunction.

1.0 Introduction

1.1 Study objectives: The primary objective is to determine the efficacy of dupilumab use plus standard of care management in patients hospitalized with moderate to severe COVID-19 infection compared to placebo plus standard of care management assessed by the proportion of patients alive and free of invasive mechanical ventilation at 28 days. The secondary objectives are to: (1) evaluate the safety of Dupilumab use in terms of eosinophilia in patients hospitalized with moderate to severe COVID-19 infection, (2) compare clinical outcomes on Dupilumab versus placebo across a range of secondary clinical safety and efficacy domains, and (3) evaluate the immunologic and biologic end points of inhibition of type 2 inflammation.

1.2 Study design: This is a randomized, double-blind, placebo-controlled, superiority phase IIa trial to assess the safety and efficacy of dupilumab use in hospitalized patients with moderate to severe COVID-19 infection. A total of 40 eligible subject will be enrolled and randomized in a 1:1 ratio to receive either dupilumab or placebo, stratifying on the disease severity measured by the required oxygen $\leq 15\text{L}$ or $> 15\text{L}$ by nasal cannula. Both arms will receive standard of care management per current National Institutes of Health (NIH) COVID-19 treatment guidelines (<https://covid19treatmentguidelines.nih.gov/>) in addition to their randomized treatments. Patients will be followed prospectively for up to 60 days after enrollment.

1.3 Database Sources: Completed forms and electronic data will be entered into the data management system in the REDCap platform. Only authorized individuals shall have access to electronic CRFs.

1.4 Randomization:

In this randomized, double-blind, placebo-controlled Phase IIa trial, a total of 40 eligible subjects will be enrolled and randomized in a 1:1 ratio to receive either dupilumab or placebo, stratifying on the disease severity, which is measured by the required oxygen $\leq 15\text{L}$ or $> 15\text{L}$ by nasal cannula. Both arms will receive standard of care management per current National Institutes of Health (NIH) COVID-19 treatment guidelines (<https://covid19treatmentguidelines.nih.gov/>) in addition to their randomized treatments.

Since this is a small trial, simple randomization procedure may result by chance in the compositions of the study arms being markedly different with respect to factors that may affect the outcome measures in the trial, or markedly unequal numbers of participants may be recruited to each arm. Further, disease severity measured by the required oxygen $\leq 15\text{L}$ or $> 15\text{L}$ by nasal cannula may impact on the outcomes differentially. Thus, to ensure the

balance of treatment allocation in disease severity, the blocked randomization with block size of 4 will be performed, stratifying based on disease severity: patients who are on 15L or less of oxygen by nasal cannula (severity group A) and those requiring more than 15L of oxygen by nasal cannula including any noninvasive ventilation measures (severity group B). Thus, separate randomization lists will be generated for mild and severe patients, using the Proc Plan procedure in SAS, and the complete randomization lists will be sent to UVA Pharmacy only to ensure the blindness for others.

Example list for mild disease group:

Disease Severity	Order	Treatment Arm	Subject Initial	SubjectID	Date of Randomization	Randomized By
Mild	101	A				
Mild	102	A				
Mild	103	B				
Mild	104	B				
Mild	105	B				
Mild	106	A				
Mild	107	A				
Mild	108	B				

1.5 Study population:

Adult patients (18 years of age or older) who are hospitalized with a positive RT-PCR for SARS-CoV-2 within the last 14 days, with illness duration within the last 14 days, and evidence of moderate to severe COVID-19 infection as defined by NIH COVID-19 Severity Categorization (see the Appendix of study protocol):

- Moderate illness: Individuals who show evidence of lower respiratory disease during clinical assessment or imaging and who have saturation of oxygen $\text{SpO}_2 \geq 94\%$ on room air at sea level.
- Severe illness: Individuals who have $\text{SpO}_2 < 94\%$ on room air at sea level, a ratio of arterial partial pressure of oxygen to fraction of inspired oxygen ($\text{PaO}_2/\text{FiO}_2$) $< 300 \text{ mm Hg}$, respiratory frequency $> 30 \text{ breaths/min}$, or lung infiltrates $> 50\%$.

Inclusion Criteria

- Male or female 18 years of age or older at the time of enrollment.
- Patients hospitalized with a positive RT-PCR for SARS-CoV-2 within the last 14 days, with illness duration within the last 14 days, and evidence of moderate to severe COVID-19 infection as defined by NIH COVID-19 Severity Categorization (8):
 - Moderate illness: Individuals who show evidence of lower respiratory disease during clinical assessment or imaging and who have saturation of oxygen $\text{SpO}_2 \geq 94\%$ on room air at sea level.
 - Severe illness: Individuals who have $\text{SpO}_2 < 94\%$ on room air at sea level, a ratio of

arterial partial pressure of oxygen to fraction of inspired oxygen ($\text{PaO}_2/\text{FiO}_2$) <300 mm Hg, respiratory frequency >30 breaths/min, or lung infiltrates $>50\%$.

- Patient and/or legally authorized representative is willing and able to provide written informed consent and comply with all protocol requirements.
- Patients with hematologic malignancies or solid tumors are eligible.
- Patients with autoimmune disorders are eligible.
- Patients with immunodeficiency and organ or stem cell transplant recipients are eligible.
- Patients with acute or chronic renal injury/failure are eligible.
- Patients with neutropenia/lymphopenia are eligible.
- Patients with elevated liver function tests are eligible.
- Women who are not taking contraception are eligible.
- Patients who are currently or have recently received steroids and/or remdesivir are eligible.
- Patient agrees to not participate in another clinical trial for the treatment of COVID-19 through end of study period.

Exclusion Criteria

- Patients who do not require inpatient admission for COVID-19 infection.
- Patients who require invasive mechanical ventilation at time of enrollment.
- A pre-existing condition or use of a medication that, in the opinion of the site investigator, may place the individual at a substantially increased risk due to study participation.
- Pregnancy or breast feeding (lactating women who agree to discard breast milk from day 1 until two weeks after the last study product is given are not excluded).
- Allergy to Dupilumab or its excipients.
- Current acute parasitic helminth infection or history of chronic parasitic infection.
- History of ocular scleritis, uveitis, keratitis or recent (<6 months) eye injury (chemical or traumatic), infection or vascular occlusion.
- Have received any live vaccine (that is, live attenuated) within 4 weeks before screening, or intend to receive a live vaccine (or live attenuated) during the study. *Note: Use of non-live (inactivated) vaccinations is allowed for all subjects.*

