### **3.2 Experience with the use of dupilumab in COVID-19**

Dupilumab, an anti-interleukin-4 receptor- $\alpha$  monoclonal antibody, leading to blockage of IL-4 and IL-13 signaling, has been FDA approved for treatment of moderate to severe atopic dermatitis since 2017. It has been successfully shown to reduce disease severity in not only those with atopic dermatitis but in other allergic diseases where Th2 cytokines have been implicated, including asthma and chronic rhinosinusitis. Original clinical trials noted excellent safety profiles in addition to favorability in its use when considering the negative impacts of long term steroid use in these patients.

We have previously conducted a phase IIa randomized double-blind placebo-controlled trial to assess the safety and efficacy of dupilumab plus standard of care versus placebo plus standard of care in mitigating respiratory failure and death in those hospitalized with COVID-19. Subjects were followed prospectively for 60 days, with collection of clinical outcomes, adverse events and immunologic biomarkers at multiple time points throughout the study period. Through this trial we found that dupilumab was safe to use for this indication, that there was reduced 60-day mortality in those who received dupilumab compared to placebo and that there was a trend toward reduction in ICU admission in the dupilumab group, all of which implicated dupilumab as a promising treatment for those hospitalized with moderate to severe COVID-19.

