## **5.0 STUDY TIMELINE**

### Telephone call to discuss follow up visit on Day 365 $\pm$ 90 days after enrollment for HSR 210184:

1. Discuss and consent for follow up visit and procedures
2. Schedule follow up visit

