- Proportion of patients alive and free of invasive mechanical ventilation at 90 days.
- Proportion of patients alive and free of invasive mechanical ventilation at 120 days.
- Proportion of patients alive and free of invasive mechanical ventilation at 150 days.
- Proportion of patients alive and free of invasive mechanical ventilation at 180 days.
- Proportion of patients alive and free of invasive mechanical ventilation at 270 days.
- Proportion of patients alive and free of invasive mechanical ventilation at 360 days.
- National Institute of Allergy and Infectious Diseases (NIAID) 8-point ordinal scale (see Appendix): Day 0, 2, 5, 7, 14, 28, 60, 180 and 360.
- Need for vasopressors
- Need for renal replacement therapy
- Need for extracorporeal membrane oxygenation (ECMO)

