- The response of being alive and free invasive mechanical ventilation at 60 days is a binary response and will be analyzed using the same methods as that for the primary efficacy outcome.
- National Institute of Allergy and Infectious Diseases (NIAID) 8-point ordinal scale on Day 0, 2, 5, 7, 14, 28, 60, 180 and 360 will be considered as longitudinal data. The distributions of the data will be examined visually first and further collapsing will be considered. Collapsed data will be analyzed in the generalized linear mixed effect model or multinomial logistic regression with the generalized estimating equation approach.
- Proportion of patients alive and free of invasive mechanical ventilation at 60, 90, 120, 150, 180, 270 and 360 days will be estimated from the Kaplan-Meier survival for the time to mechanical ventilation-free survival over the first year. The difference in these proportions between the two treatment groups will be evaluated by the log-rank test and further in Cox regression adjusting for the baseline covariates. For the analysis of mortality over the first year, additional adjustment for dynamic mechanical ventilation effect will be considered by including being on ventilation as a time-vary covariate in the Cox regression.
- Need for vasopressors is a binary response and will be analyzed using the same methods as for the primary efficacy outcome.
- Need for renal replacement therapy is a binary response and will be analyzed using the same methods as for the primary efficacy outcome.
- Need for extracorporeal membrane oxygenation (ECMO) is a binary response and will be analyzed using the same methods as for the primary efficacy outcome.

6.0 Other safety analyses:

Analysis of adverse event (AE) data will primarily be descriptive based on CTCAE coding of events. The proportion of subjects experiencing a severe AE and the proportion experiencing a Grade 3 or higher will be recorded. AE will be compared to published data.

7.0 Sample size estimation and power analysis:

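### SAP 1.2 ends follow-up at 60 days, but SAP 2.2.2 and 5.3.2 require outcomes to Day 360, and no source is named for vital or ventilation status after Day 60

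*SAP*

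**What the plan says.** **Length of follow-up.** SAP 1.2 says: "Patients will be followed prospectively for up to 60 days after enrollment". Protocol 3.2, looking back on the parent trial, agrees: "Subjects were followed prospectively for 60 days".

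**Outcomes that need longer follow-up.** SAP 2.2.2 lists a series of secondary outcomes that runs from "Proportion of patients alive and free of invasive mechanical ventilation at 90 days" to "Proportion of patients alive and free of invasive mechanical ventilation at 360 days", with 120, 150, 180 and 270 days in between. It schedules the NIAID ordinal scale on "Day 0, 2, 5, 7, 14, 28, 60, 180 and 360". SAP 5.3.2 says the ventilation-free proportions will be "estimated from the Kaplan-Meier survival for the time to mechanical ventilation-free survival over the first year", compared by log-rank test and Cox regression. For first-year mortality it adds ventilation as a time-varying covariate.

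**Unknown status.** SAP 8.0 counts withdrawals with unknown status as events, but only for Day 28. Other outcomes are left to a missing-at-random assumption, with sensitivity analyses for selected ones.

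**The extension.** Protocol 5.0 plans a "Telephone call to discuss follow up visit on Day 365" (plus or minus 90 days), to obtain consent and book a single visit in the same window. Protocol 4.2 excludes parent-trial patients who have died or who cannot or will not attend. Neither the visit items in Protocol 5.0 nor the endpoints in 7.1 include vital status, ventilation or the ordinal scale. The scale is printed in the appendix without a schedule.

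**The concern.** The SAP sets an end of follow-up and then asks for results up to 300 days past it (360 - 60). A team working to 1.2 would stop collecting at Day 60 and could still fill every row of the late-outcome table, because Kaplan-Meier software can carry the last estimate forward. The Day 90 to 360 figures would look like one-year results while containing no information beyond Day 60.

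A team working to 2.2.2 and 5.3.2 would have to find later status somewhere, and the supplied documents do not say where, for whom, or when a patient is censored. The nearest available contact is the extension visit, which by design omits patients who died after Day 60. Taking status from its attenders alone would be selective. The time-varying ventilation term would also need dates of ventilation through the year, which no supplied schedule collects.

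**Working it through.** **1. The plan's own figure.** SAP 7.0 gives 75% power at Day 28 for 79.5% versus 97.2%, 40 patients in total, one-sided alpha 0.10, score test. With 20 per arm (1:1), x successes on placebo and y on dupilumab, and p the pooled proportion (x + y)/40, the test rejects when

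[(y - x)/20] / sqrt[p(1 - p) × 2/20] ≥ the 90th percentile of the standard normal.

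Summing the binomial probabilities of all rejecting outcomes gives **75.1%**, which reproduces the stated 75%. (A normal approximation gives 68.5% and the unpooled version 70.3%; the exact power of the named test is the one that matches.) None of these inputs depends on anything after Day 28.

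**2. Time points against follow-up.**

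| Outcome | Days required | After Day 60 |
|---|---|---|
| Ventilation-free survival (Kaplan-Meier) | 60, 90, 120, 150, 180, 270, 360 | 6 of 7 |
| Ordinal scale | 0, 2, 5, 7, 14, 28, 60, 180, 360 | 2 of 9 |
| Mortality over the first year (Cox) | through the first year | all time after Day 60 |

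**3. Patients whose later status is open.** Protocol 6.2: 40 enrolled, 7 dead by Day 60, so 40 - 7 = **33** survivors. The 7 deaths (7/40 = 17.5%) count as failures at every later day.

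**4. What the estimator does.** For t > 60,

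S(t) = S(60) × product over event times in (60, t] of (1 - d/n).

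If all survivors are censored at Day 60, n = 0 afterwards and there are no factors, so S(t) is either undefined or equal to S(60). The log-rank statistic and the Cox partial likelihood are built from event times only. The first-year analyses would therefore be the Day 60 analyses under another name.

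**5. How wide the ignorance is.** Survival at Day 60 is 33/40 = 82.5% (exact 95% CI 67.2% to 92.7%). This is an upper limit for ventilation-free survival, since the documents do not give the number ventilated by then. With no later data, the pooled proportion at any day from 90 to 360 is bounded only by 0/40 = **0%** and 33/40 = **82.5%**. With 20 per arm, one patient's status is worth 1/20 = 5 points within an arm.

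**6. Whether the extension visit supplies the data.** Its window is 365 - 90 = Day 275 to 365 + 90 = Day 455. It opens after the 90, 120, 150, 180 and 270 day points, so it could inform those only in retrospect. As an illustration, assume m of the 33 attend and all are alive and ventilation-free:

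| m | 7 deaths plus attenders | Attenders only |
|---|---|---|
| 10 | 10/17 = 58.8% | 100% |
| 20 | 20/27 = 74.1% | 100% |
| 33 | 33/40 = 82.5% | 100% |

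The answer depends on how non-attenders are handled, and the SAP does not say.

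**The case against.** The best defence is that one-year follow-up was plainly intended. The SAP schedules an ordinal scale that records death and invasive ventilation at Days 180 and 360, and it plans first-year time-to-event models. On that reading 1.2 is a sentence left behind when the outcomes were extended. Further, the SAP belongs to the parent trial, whose own protocol is not among the supplied documents, and later ascertainment may be described there. Protocol 3.2 is a background summary, not a schedule. The outcomes concerned are secondary, in a study that calls itself exploratory, and SAP 8.0 allows for missing secondary data.

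Much of this stands. It explains how the contradiction arose and limits its importance. It does not remove it: the governing sentence still says 60 days, and in the supplied documents the data source, the censoring rule and the handling of unknown late status are all absent. SAP 8.0 deals with planned observations that go missing, not with observations no one is told to make.

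Three stronger readings are tempting, and the documents do not support them:

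- A reader might infer that the late proportions have no observations at all. Deaths, and first ventilation events, by Day 60 still count at every later day. What is open is the later status of up to 33 survivors.
- A reader might infer that the results will rest on those who return at one year and so overstate survival. Nothing in either document makes extension attenders the source. The illustration above shows the result can fall below or above the 82.5% ceiling, depending on handling.
- A reader might fault a last contact at Day 275 for leaving Day 360 unknown. That is ordinary censoring, which Kaplan-Meier handles.

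**Conclusion.** The point holds as an internal contradiction in the SAP: 1.2 against 2.2.2 and 5.3.2. Read literally, six of the seven Kaplan-Meier time points and two of the nine ordinal-scale assessments fall after follow-up ends. No survivor is then at risk, and the later estimates repeat the Day 60 value. The missing information concerns up to 33 of 40 patients, with bounds of 0% to 82.5% on the pooled late proportion.

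This rests on 7 deaths by Day 60 as stated in Protocol 6.2, on equal arms of 20 for the 5-point figure, and on the supplied documents only. They do not show that later data were not collected, only that no source is described. The Day 28 primary endpoint and its 75% power are untouched. The SAP should be corrected before any one-year result is reported.

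**What to change.** 1. Change SAP 1.2 to follow-up through Day 360 for vital and ventilation status.
2. State the source: medical record review for all 40 randomised patients, supplemented by the telephone contact already planned in Protocol 5.0 where consent allows. Record dates of death and of the start and end of ventilation, so that the time-varying term can be fitted.
3. Add to SAP 5.3.2 that patients are censored at the date status was last known, and to SAP 8.0 how unknown status after Day 60 is handled.
4. Keep the ordinal scale at Days 180 and 360 only where status on that day can be established. A single call around one year cannot reliably recover a Day 180 score.
5. If this cannot be done, delete the Day 90 to 360 outcomes and limit the time-to-event analysis to 60 days.

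The cost is a few sentences in the SAP, a matching line in the protocol, a record check for up to 33 survivors and an added item in an existing call. Consent cover must be confirmed for patients who decline the extension, so the cost is somewhat more than wording alone. Nothing changes for the primary endpoint or the sample size.
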